16. Subject concurrently participates or participated in a drug, drug/device, or biologic investigational research study within 3 months or 5 half-lives of the IP, whichever is longer, prior to the first dose.
- 17.2 Subject has a history or presence of cardiopathy, or clinically significant abnormalities detected on 12-lead ECG of either rhythm or conduction e.g. repeated demonstration of a QTcF >450 ms detected on the 12-lead ECG or a history of additional risk factors for TdP (e.g. heart failure, family history of long QT syndrome, hypokalemia and other electrolyte disorders). A first-degree atrioventricular block will not be considered as a significant abnormality.
18. History of organ or bone marrow transplant.
19. Female subject is pregnant or breast feeding or intending to become pregnant or breastfeed during the study.

20.1 Subject was vaccinated with a live attenuated vaccine within 60 days prior to screening.

21.1 Subject has severe organ manifestation or life-threatening condition, or has planned a surgery during the study.

22.2 Subject has any of the following laboratory abnormalities:

- aspartate aminotransferase (AST) >2 times the upper limit of normal (ULN)
- alanine aminotransferase (ALT) >2 times the ULN
- total bilirubin >2 times the ULN
- prothrombin time or partial thromboplastin time > ULN.
- serum potassium concentration <3.5 mmol/L

23. Subject is institutionalized by virtue of an order issued by either the judicial or the administrative authorities or has a dependency on the sponsor or investigator.

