- Arrhythmia or conduction abnormality, including but not limited to prolonged QTcF, where the severity is categorized as Common Terminology Criteria for Adverse Events (CTCAE) Grade 3 or higher (QTc > 500 ms and/or 60 ms over baseline on at least 2 separate ECGs 5 minutes apart) or clinically significant arrhythmia of any grade.
- Liver enzyme increase (see also [Appendix 15](#))
 - AST and/or ALT ≥ 8 times the ULN.
 - AST and/or ALT elevations ≥ 3 times ULN with signs of liver damage (i.e. with the appearance of fatigue, nausea, vomiting, right upper quadrant pain or tenderness, fever, rash and/or eosinophilia [$> 5\%$], and/or total bilirubin ≥ 2.0 times ULN or international normalized ratio [INR] > 1.5).
 - In addition, a dose interruption or reduction (if applicable) should be considered if AST and/or ALT ≥ 3 times ULN and < 5 times ULN and dosing with IP should be interrupted if AST and/or ALT ≥ 5 and < 8 times ULN.

For subjects having:

- AST or ALT ≥ 8 times ULN.
- AST or ALT ≥ 3 times ULN with signs of liver damage (i.e. with the appearance of fatigue, nausea, vomiting, right upper quadrant pain or tenderness, fever, rash, and/or

eosinophilia [>5%], and/or total bilirubin $\geq 1.5 \times \text{ULN}$ or INR > 1.5). These cases should be reported as SAEs.

the following steps will need to be performed by the investigator:

- The site should immediately contact the subject and require the subject to discontinue IP immediately. The subject should be asked to return to the site within a 48-hour window from awareness of the result.
- A full evaluation of various causes of hepatitis should be conducted (i.e. infectious, alcohol, medications, anatomical).
- An assessment of other concomitant medications and SoC should be made. The investigator should consider to whether it is in the best interest of the subject to stop/interrupt concomitant medications and SoC treatment.
- A detailed history including relevant information on alcohol use, recreational drug use, supplement consumption, any herbal remedies, family history, sexual history, travel history, history of contact with a jaundiced subject, surgery, occupational history, blood transfusion, history of liver or allergic disease, and any other potential causes attributable to a liver insult should be collected.

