11.1.4. Adverse Events of Special Interest

Not applicable.

11.1.5. Clinical Laboratory Abnormalities and Other Abnormal Assessments as Adverse Events or Serious Adverse Events

Laboratory abnormalities without clinical significance based on the investigator's judgment are not considered AEs or SAEs. However, laboratory abnormalities (e.g. clinical chemistry, hematology, and urinalysis) or other abnormal (clinical study-specific) assessments (e.g. ECG, radiography, vital signs) that require medical or surgical intervention, are associated with signs and/or symptoms, and/or lead to IP interruption, modification or discontinuation must be recorded as an AE or SAE if they meet the definition as described in Sections 11.1.1 and 11.1.2, respectively. If the laboratory abnormality is part of a syndrome, the syndrome or diagnosis is to be reported (e.g. anemia instead of decreased hemoglobin).

The following liver enzyme elevations must be reported as SAEs:

- AST or ALT $\geq 3 \times \text{ULN}$ with signs of liver damage (total bilirubin $> 2 \times \text{ULN}$ OR INR > 1.5 , and/or with the appearance of fatigue, nausea, vomiting, right upper quadrant pain or tenderness, fever, rash and/or eosinophilia [$> 5\%$]).

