11.3.2. Serious Adverse Events

Subjects experiencing an SAE or an emergency situation will be examined by a physician as soon as possible. The subject will remain under observation as long as medically indicated.

Appropriate laboratory tests will be performed until all parameters return to normal or are otherwise explained or stable.

All SAEs, whether or not deemed IP-related, must be recorded on the SAE form and in the CRF. The investigator must report each SAE immediately, and under no circumstances should this exceed 24 hours following the knowledge of the SAE, as is indicated on page 2 under “Emergency Contact Information”.

The SAE form should at least contain identifiers of the subject and the reporter, SAE term and statement of relatedness to the IP, and at a later stage if not yet available within 24 hours, the form needs to be completed with a clearly written narrative describing signs, symptoms, and treatment of the event, diagnostic procedures, as well as any relevant laboratory data and any sequelae.

FU and outcomes should be reported and documented in the source documents for all subjects that experience an SAE. It is important that the information provided on the SAE form matches the information recorded on the CRF for the same event.

Copies of additional laboratory tests, consultation reports, post-mortem reports, hospital case reports, autopsy reports, and other documents should be sent when requested and available. Only subject identifiers (subject number) should appear on the copies, and all names and initials should be blackened and rendered illegible. Follow-up (FU) reports relative to the subject’s subsequent course must be submitted until the event has subsided or, in case of permanent impairment, until the condition stabilizes.

Any SAEs that occur after the post-treatment FU visit but within 30 days of the last dose of IP(s), regardless of causality, should also be reported (Emergency Contact Information on Page 2) but not entered in the CRF. Investigators are not obligated to actively seek SAEs after the CSP-defined FU period. However, if the investigator is informed about an SAE that occurs at any time

after the subjects' post-treatment FU visit and the event is deemed relevant to the use of IP(s), he/she should promptly document and report the event to the sponsor by using the SAE form.

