Appendix 15: Algorithm for Elevated Liver Function Tests

	AST or ALT increase to				
Value Range	>=1.5x to 3xULN	>=3x to <5xULN	>=5x to <8xULN	>=3xULN with signs of liver damage ¹	>=8xULN
IP Action	Continue as planned	Reduce or interrupt IP for at least 2 weeks	Interrupt IP for at least 2 weeks	Discontinue IP ²	Discontinue IP ²
		Close observation ²	Close observation ²		
After at least 2 weeks	AST and ALT <3xULN	AST or ALT >=3xULN			
	Weekly LFTs for the first 2 weeks (biweekly for the following weeks, or more frequently at investigator's discretion)	Discontinue IP Report SAE and complete liver event page for any of abnormalities listed below ³ : - AST/ALT increase >=3xULN with signs of liver damage ¹			

¹ Signs of liver damage:

- total bilirubin >=2.0xULN OR INR >1.5, and/or
- symptoms: appearance of fatigue, nausea, vomiting, right upper abdominal quadrant pain or tenderness, fever, rash and/or eosinophilia (>5%)

² Close observation recommendations:

- Monitor 2 to 3 times per week all of the following parameters: ALT, AST, alkaline phosphatase, total bilirubin, eosinophils, INR. If local regulations allow, home visits can be performed if subjects cannot come to the clinical study center.
- Frequency of retesting can be reduced to once a week or less if abnormalities stabilize or the IP has been discontinued; however, monitoring might still be needed more frequently taking into consideration the SoC and/or changes to this.
- Based upon investigator's discretion gastroenterology or hepatology consultations, additional serology testing, imaging, and pathology assessments may be required.
- Re-query history of symptoms, prior and concurrent diseases, concomitant medication and non-prescription medicines, herbal, dietary supplements, alcohol use, recreational drug use, special diets.

- Rule out all of the following: acute viral hepatitis, autoimmune hepatitis, alcoholic hepatitis, non-alcoholic fatty hepatitis, hypoxic/ischemic hepatitis, biliary tract disease, and cholestasis.

- Re-query exposure to environmental chemical agents.

³ The following steps should be followed:

- The site should immediately contact the subject and require the subject to discontinue IP immediately. The subject should be asked to return to the site within a 48-hour window from awareness of the result.
- A full evaluation of various causes of hepatitis should be conducted (i.e. infectious, alcohol, medications, anatomical).

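### The bilirubin level that counts as liver damage at AST/ALT ≥3 × ULN differs between Protocol 6.4, 11.1.5 and Appendix 15, so cases at 1.5 to <2.0 × ULN get conflicting instructions on stopping IP and on SAE reporting

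*Protocol*

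**What the plan says.** Four places in the current protocol define a liver-damage sign that applies once AST or ALT reaches 3 × ULN.

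- **6.4, first list** (conditions under which IP must be stopped): bilirubin at 2.0 "times ULN or international normalized ratio [INR"] above 1.5, alongside listed symptoms and eosinophilia. Without such a sign, 6.4 asks that interruption or reduction be considered at AST/ALT 3 to <5 × ULN, and that dosing be interrupted at 5 to <8 × ULN.
- **6.4, second list** (cases needing follow-up steps): bilirubin ≥1.5 × ULN "or INR > 1.5). These cases should be reported as SAEs". The first step is "The site should immediately contact the subject and require the subject to discontinue IP immediately".
- **11.1.5**: "The following liver enzyme elevations must be reported as SAEs", with bilirubin >2 × ULN.
- **Appendix 15, footnote 1**: "total bilirubin >=2.0xULN OR INR >1.5", leading to discontinuation and an SAE report. Without a sign, the action at 3 to <5 × ULN is "Reduce or interrupt IP for at least 2 weeks", and at 5 to <8 × ULN it is interruption for at least 2 weeks.

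The symptom list, the eosinophil limit (>5%) and the INR limit (>1.5) are the same in all four. Only bilirubin differs. Section 6.4 cross-refers to Appendix 15, but nothing ranks the versions.

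**The concern.** Two sites following the protocol in good faith could manage the same patient differently. One stops IP permanently and files an SAE, for which 11.3.2 says "under no circumstances should this exceed 24 hours following the knowledge of the SAE". The other reduces or interrupts IP, may later resume it, and files nothing.

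The first stake is patient safety. The second is the safety result: TEAEs are a primary endpoint, and SAP 6.3.1.8 tabulates serious TEAEs and TEAEs leading to IP discontinuation, so counts could depend on which section a site read. The third is the efficacy estimate. Protocol 5.6 and SAP 3 handle early treatment discontinuation by the hypothetical strategy, and SAP 4.4.1.2 does not use non-PK data from more than 7 days after the last dose for on-treatment visits. Whether IP is stopped or interrupted can therefore decide whether a subject's later ESSDAI values enter the model.

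**Working it through.** There is no sample-size or power figure to reproduce. The check applies each rule to the same patient.

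**Held fixed:** no listed symptom, INR ≤1.5, eosinophils ≤5%. Bilirubin is then the deciding sign.

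**Rules at AST/ALT ≥3 × ULN (bilirubin b, in multiples of ULN):**

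| Place | Sign is met when | Governs |
|---|---|---|
| 6.4 first list | b ≥ 2.0 | stopping IP |
| 6.4 second list | b ≥ 1.5 | stopping IP and SAE |
| 11.1.5 | b > 2 | SAE |
| Appendix 15 | b ≥ 2.0 | stopping IP and SAE |

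**Result by bilirubin band:**

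| Bilirubin | 6.4 first | 6.4 second | 11.1.5 | Appendix 15 | Stopping IP (AST/ALT 3 to <8) | SAE (AST/ALT ≥3) |
|---|---|---|---|---|---|---|
| <1.5 | no | no | no | no | agree | agree |
| 1.5 to <2.0 | no | yes | no | no | **conflict** | **conflict** |
| exactly 2.0 | yes | yes | no | yes | agree | **conflict** |
| >2.0 | yes | yes | yes | yes | agree | agree |

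At AST/ALT ≥8 × ULN, both 6.4 lists and Appendix 15 stop IP whatever the bilirubin, so the conflict on stopping ends there.

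**Worked case:** ALT 3.5 × ULN, bilirubin 1.7 × ULN, INR 1.0, no other sign.

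- 6.4 second list: 1.7 ≥ 1.5, so stop IP at once and report an SAE.
- 6.4 first list: 1.7 < 2.0, so not met; 3.5 lies in 3 to <5, so consider interruption or reduction.
- Appendix 15: 1.7 < 2.0, so not met; reduce or interrupt for at least 2 weeks, with no SAE on this ground.
- 11.1.5: 1.7 is not above 2, so no SAE is required.

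With ALT 6 × ULN and the same bilirubin, the second list still stops IP and requires an SAE report, while the first list and Appendix 15 interrupt.

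**Scale.** The documents give no rate for this combination, so no expected number of cases can be stated. One case is 1/20 = 5% of the planned active arm or 1/10 = 10% of the planned placebo arm.

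**Does aligning bilirubin alone settle the worked case?** With ≥1.5 everywhere, yes: all places stop IP and report. With ≥2.0 everywhere, no: 6.4 would still only ask that interruption or reduction be considered, while Appendix 15 would direct it. The action at 3 to <5 × ULN has to be aligned as well.

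**The case against.** The best defence is that the rules are cumulative. Section 11.1.5 says what must be reported and forbids no other report. The first 6.4 list says when IP must stop, not when it may not. Section 6.4 also lets the investigator stop treatment over safety concerns. A site that follows the strictest text breaches neither provision. That much stands.

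It does not remove the clash with Appendix 15, whose discontinuation and SAE column excludes the worked case and whose applicable band allows IP to be resumed. The protocol nowhere tells sites to take the strictest version, and 6.4 urges keeping subjects on treatment where possible. A site working from Appendix 15 or 11.1.5 alone never sees 1.5.

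It is also fair that >2 and ≥2.0 differ only at exactly 2.0 × ULN. In practice there is one outlying value, 1.5, against 2.0.

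A reader might infer that eligible subjects could meet the second list at entry, because exclusion 22.2 removes only "total bilirubin >2 times the ULN". The documents do not support this. The sign counts only with AST/ALT ≥3 × ULN, and the same criterion excludes AST or ALT >2 × ULN.

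A reader might also link the inconsistency to the study's termination for a liver toxicity signal (SAP 1). Nothing in the documents shows that it contributed. The termination shows only that the liver rules mattered in this trial.

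**Conclusion.** The protocol is wrong as written, in a narrow but consequential band. When bilirubin is the only sign, cases at 1.5 to <2.0 × ULN get conflicting instructions on stopping IP at AST/ALT 3 to <8 × ULN, and on SAE reporting at AST/ALT ≥3 × ULN. At exactly 2.0 × ULN only the SAE instruction conflicts. Below 1.5 and above 2.0 all four places agree, and where another listed sign is present the difference has no effect.

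This rests on the current, unredacted text and on the absence of any precedence rule in it. How often the band would occur, and how far the treatment estimate would move, cannot be derived from the documents; the effect on the primary analysis is a mechanism, not an estimate. The tabulations in SAP 6.3.2.8 (AST or ALT >3 × ULN with bilirubin >1.5 or >2 × ULN) are analysis categories and do not settle what a site should do.

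**What to change.** Use one bilirubin threshold, with the same inequality, in both 6.4 lists, 11.1.5 and Appendix 15. The documents do not decide which value; that is the sponsor's clinical choice.

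- **≥2.0 × ULN:** two threshold edits (6.4 second list, 11.1.5). Downside: cases at 1.5 to <2.0 × ULN with AST/ALT below 8 × ULN are interrupted or reduced rather than stopped, and are not SAEs on this ground.
- **≥1.5 × ULN:** three threshold edits (6.4 first list, 11.1.5, Appendix 15). More cautious. Downside: a few more permanent stops and SAE reports.

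In the same edit, make the action at AST/ALT 3 to <5 × ULN identical in 6.4 and Appendix 15: either considered or required, with the same minimum duration.

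Neither option needs a change to the SAP tabulations. Because the study has been terminated, the wording change mainly serves any reuse of this protocol text. For the present trial, the sponsor can check whether any subject fell in the affected band and, if so, whether the stopping decision and SAE classification were handled consistently across sites.

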6.5. Measures to Minimize Bias

6.5.1. Randomization

At screening, subjects will be assigned a subject identification number. When a subject is confirmed to be eligible for the clinical study, the subject will be randomized. Allocation of each subject to a given treatment will be done using a centralized electronic system (interactive web response system [IWRS]). Subjects will be randomized in a 2:1 ratio to GLPG3970 or placebo.

6.5.2. Blinding and Unblinding

This is a randomized, double-blind clinical study. The subjects and the entire clinical study team, including the investigators, clinical study coordinators, and sponsor personnel, except for the Safety Monitoring Committee, are blinded to treatment assignment.

Blinded and packaged medication will be provided to the site. All IP formulations will be identical in appearance, shape, smell and taste, and will be packaged in the proper proportion to assure desired dosages and maintenance of the blinding.

The blind can be broken only if the investigator deems it necessary for the safety of a subject. The investigator is encouraged to discuss considerations to break the blind with the medical leader of the study, whenever possible and where the situation allows. However, the responsibility to break the treatment code in emergency situations resides solely with the investigator. The investigator is not required to discuss unblinding beforehand if he or she feels rapid emergency unblinding is necessary, but is required to inform the sponsor in within 24 hours after unblinding has occurred.

The blind can be broken by the investigator via IWRS.

If the blind is broken for any reason during the course of the clinical study, the moment on which the blind was broken, and all other relevant information will be documented by the site. The reason for breaking the blind will be indicated and justified in the source documentation.

If an AE leads to unblinding, the AE will be given as the reason for unblinding. All subjects who are unblinded should, where possible, complete the FU visit assessments 28±3 days after last IP dosing. Any AEs will be followed until resolution.

The code-break information (via IWRS vendor) will be provided to the bioanalytical laboratory responsible for PK sample analysis, the sponsor person responsible for providing unblinded data to the Safety Monitoring Committee, the CRO responsible for the population PK (pop-PK) [REDACTED], and to the pharmacovigilance vendor for SAE reporting purposes.

7. INVESTIGATIONAL PRODUCTS

7.1. Identity of the Investigational Products

GLPG3970 will be supplied to the pharmacist of the study site or to the hospital pharmacy, by and under the responsibility of the sponsor, who will also provide the investigator and pharmacist (or appropriate qualified member of the clinical study staff) with appropriate certificates of analytical conformity and European Union (EU) Qualified Person release documents.

Matching placebo tablets will also be provided.

For more details on the composition of the IP refer to the latest version of the IB and its relevant updates/addenda.

7.2. Dosage and Administration

GLPG3970 will be provided as a film-coated tablet containing 200 mg of the active pharmaceutical ingredient G1567970 (G1567970 is the compound code for GLPG3970). A dose of 400 mg (2 x 200 mg tablets) q.d. will be taken orally.

At all dosing days, the IP needs to be taken q.d. at approximately the same time every morning in a fed state (together with a meal), except at Visit 1 (Day 1) when the IP will be taken in a fasted state. At Visit 1 (Day 1), breakfast will be provided to the subject 0.5-1 hour after the IP intake and lunch should be eaten 1 hour before or after the ECG measurement at 4.5 hours postdose. Subjects will be instructed to swallow the tablets of GLPG3970 or placebo as a whole with a glass of water and to not chew the drug prior to swallowing. At Visit 1 (Day 1), IP will be administered on site after predose assessments have been completed. At Visit 2, 3, 4, and 5, subjects also need to take their IP on site.

Subjects will receive tablets to take home. Instructions for dosing and storage are incorporated in the IP labels.

If a subject misses a dose (e.g. because he/she forgot to take the medication), he/she should take the missed dose within 12 hours after the planned intake time. If IP is not taken within 12 hours

after the planned time, the missed dose should be skipped. For each dose taken at home, the time, date, and number of tablets taken should be recorded in the subject's diary card.

7.3. Packaging, Labeling and Distribution

IP packages will be labeled with clinical study-specific details, including storage conditions.

All manufacturing, packaging, and labeling operations will be performed according to Good Manufacturing Practice for Medicinal Products and the relevant regulatory requirements.

Each medication kit will be identified with a unique kit number. Multiple kits can be provided to a subject at each visit, providing the subject with sufficient IP to cover the period until the next scheduled visit.

The distribution of IP to the site will only occur after the required local documentation is obtained, including clinical study approval by regulatory authorities and the IECs/IRBs, documentation on which the assessment of the investigator's qualifications was based (e.g. curriculum vitae), and the signed and dated study agreement and financial agreement.

In case of SARS-CoV-2 travel restrictions, to ensure study subjects maintain dosing per protocol requirements during this study, special delivery services through DTP shipments of IP to the subject can be implemented. DTP should only be used in case of emergency where on site IP dispensation is not possible, and if allowed per local regulations. Local guidelines must be followed and regulatory approval or notification to authorities may be required. Agreement of the subject to receive IP at home is required prior to the shipment of IP to the subject's home. The DTP process used will be reviewed and approved by the sponsor. In case the DTP shipments originates from the investigational site, they will be coordinated by the investigational site(s) in collaboration with the local CRO without the involvement of the sponsor, to ensure clinical study integrity.

